5.6 Criteria for Removal from Study

Participants will be removed from study when any of the criteria listed in Section 5.4 applies. The reason for study removal and the date the participant is removed must be documented in the study-specific case report form (CRF). Alternative care options will be discussed with the participant.

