months, compared with 9.9 months in men treated with DP plus bevacizumab (P < 0.001). In the post-docetaxel sunitinib trial, men treated with prednisone alone had median PFS of 4.1 months, compared with 5.5 months in men treated with prednisone plus sunitinib (P < 0.001). It is not clear why the PFS benefits did not translate to overall survival benefits, but one plausible explanation may relate to tolerability. In the sunitinib trial, for example, more than 25% of men discontinued due to toxicity, likely blunting any signal for positive therapeutic impact. Additionally, both trials studied unselected populations of men with mCRPC, and conceivably there are particular subgroups of men who may benefit; predictive biomarkers of antiangiogenic response have not yet been validated in this patient population.

Tivozanib is a potent tyrosine kinase inhibitor (TKI) of VEGF receptors that has shown encouraging results in renal cell carcinoma³. Among the unique features of tivozanib are its marked selectivity for the VEGF receptors¹², as well as an outstanding tolerability profile that may be directly linked to this selectivity¹. The tolerability of tivozanib suggests that combination therapy with other classes of antineoplastic agents may be more feasible than previous attempts with other TKIs. However, it is likely that combining tivozanib with cytotoxic agents will still result in exaggerated adverse effects, as has been observed with bevacizumab and other VEGF pathway inhibitors. Therefore, it is of particular interest to attempt combination therapy with other targeted agents, and in prostate cancer, specifically with AR-targeted agents. Given the non-overlapping toxicity profile of tivozanib and enz, there is an opportunity to merge additive or potentially synergistic benefits by combining them in an appropriate patient population.

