5.5 Duration of Follow Up

Patients will be followed for survival information every 3 months until death, up to 2 years after discontinuing therapy, or patient is lost to follow-up. If a patient has withdrawn consent, no further follow up will occur.

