9.1.4 Progression-Free Survival

Progression-Free Survival (PFS) is defined as the duration of time from registration to time of documented disease progression (radiographic or clinical) or death without documentation of disease progression. Patients who are alive and without evidence of progression will be censored at the date of last disease evaluation.

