14. STATISTICAL CONSIDERATIONS

14.1. Study Design/Endpoints

The phase 2 study will evaluate the efficacy of enzalutamide and tivozanib in patients with mCRPC. The primary endpoint will be progression free survival (PFS), defined as the time from registration to the earlier of progression (radiographic or clinical) or death and, if censored, the date of last disease evaluation. Based on phase 3 data, the median PFS with enzalutamide alone in chemotherapy naive mCRPC is 14 months. The hypothesis is that the addition of tivozanib will significantly enhance efficacy. An improvement of 60% to a median PFS of 22.4 months will be considered worthy of further study. Assuming exponential distribution, this implies a hazard ratio (HR) of 0.625 relative to historical control (hazard rate from 0.0495 to 0.0309). Using a one-sample exponential test, there will be 80% power to demonstrate a 60% improvement at a one-sided Type 1 error rate of 10% with enrollment of 38 patients and 20 PFS events.

Because this combination has not been previously tested, a safety run-in will be conducted at the outset of the trial. After the first 3 patients are enrolled, accrual will be held until all three patients complete the first 1 month of treatment. Additionally, after a total of 10 patients are enrolled, these patients will be analyzed for safety and toxicity by the DSMC. If any treatment-related, expected or unexpected grade 3 or higher adverse events occur during the first month of treatment in the first 3 patients, or if the rate is >30% among the first 10 patients during the first month of treatment, further accrual will be halted for reconsideration of the appropriateness of the dosing schedules.

The table below gives the probability of observing 1 or more toxicities among the first 3 patients or 3 or more among the first 10 patients given different true underlying toxicity rates.

| True toxicity rate | 1% | 10% | 20% | 30% | 40% | 50% |
|--|--------|-------|-------|-------|-------|-------|
| Probability of Stopping Early (≥ 1/3) | 0.030 | 0.271 | 0.488 | 0.657 | 0.784 | 0.875 |
| Probability of Stopping Early (≥ 3/10) | <0.001 | 0.070 | 0.322 | 0.617 | 0.832 | 0.945 |

Thus, if the true underlying proportion of toxic events is 30% at the current dosing schedules, there is a greater than 60% chance of stopping early.

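### Progression is not scheduled to be followed after a stop for toxicity or intercurrent illness, so the primary PFS test can depart from its nominal 10% error in a direction the trial cannot determine

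*Combined protocol and SAP*

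**What the plan says.** Section 5.4 lists reasons to end treatment, among them intercurrent illness and unacceptable adverse events. Section 5.6 then states: "Participants will be removed from study when any of the criteria listed in Section 5.4 applies". Sections 6.2 and 6.4 also take a man off study for unacceptable toxicity of tivozanib or enzalutamide, the latter with an exception at the principal investigator's discretion. On long dose holds the text differs: Section 5.1.2 ends study treatment, whereas Section 6.2 ends study participation, and the two also differ on a hold of exactly 4 weeks.

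Section 5.1.3 and the Section 8 calendar give one off-study visit, within 30 days of the last dose. Bone scan and CT are done then only if none was done in the previous 6 weeks. After that, Section 5.5 says: "Patients will be followed for survival information every 3 months until death, up to 2 years after discontinuing therapy". No section schedules or records tumour status beyond that visit.

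For the primary endpoint, Section 9.1.4 counts radiographic or clinical progression, or death without documented progression, and sets no limit on the gap since the last evaluation. For the rest: "Patients who are alive and without evidence of progression will be censored at the date of last disease evaluation". Section 14.1 agrees. The opening of Section 9, however, names only deaths caused by the disease when it defines disease progression.

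The test is specified in Section 14.1: "Using a one-sample exponential test, there will be 80% power to demonstrate a 60% improvement". The design sets the one-sided error at 10% and calls for 38 patients and 20 events. The reference value is that "the median PFS with enzalutamide alone in chemotherapy naive mCRPC is 14 months".

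**The concern.** A man who stops for toxicity before progressing can enter the primary analysis in two ways, and neither reflects when he progressed. If he is alive at the analysis, his time ends near the stop and his later progression, if any, is not counted. If he has died, the event is dated at death and the time between unrecorded progression and death is added to progression-free exposure.

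The one-sample exponential test depends only on the number of events and the total exposure, so both routes feed directly into it. There is no control arm in which the same distortion might partly cancel, and with 20 events a few men can change the result. The plan has no sensitivity analysis for these men. The increase from 38 to 42 in Section 14.2 is for unevaluable patients and does not address the problem. At stake is whether a positive result means what a 10% one-sided error is supposed to mean.

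**Working it through.** **1. Reproduce the stated design.** Inputs from Section 14.1: null median 14 months, alternative 22.4 months, 20 events, one-sided alpha 0.10.

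- Null hazard: ln 2 / 14 = 0.0495 per month. Alternative: ln 2 / 22.4 = 0.0309. Ratio: 14 / 22.4 = 0.625.
- Exact test: reject if 2 × 0.0495 × T exceeds the 90th percentile of chi-square with 40 df, which is 51.8. Here T is total PFS exposure. The threshold is T > 51.8 / 0.099 = 523 man-months. Expected exposure at 20 events is 20 / 0.0495 = 404 under the null and 20 / 0.0309 = 647 under the alternative.
- Power: P(chi-square with 40 df > 0.625 × 51.8 = 32.4) = 79.9%. The stated 80% is reproduced.
- Approximate events needed: (1.2816 + 0.8416)² / (ln 1.6)² = 4.508 / 0.2209 = 20.4, which agrees with 20.

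**2. How one man enters T.** A hypothetical man stops for toxicity at month 3 with a clean scan at that time, progresses in routine care at month 8 and dies at month 18.

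| Rule | Analysed after progression, before death | Analysed after death |
|---|---|---|
| Progression followed after the stop | 8 months, 1 event | 8 months, 1 event |
| Rule as written | 3 months, 0 events | 18 months, 1 event |

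If men who stop have the same hazard as the others, the written rule is conservative, because exposure after the stop is counted only for men who die. If they have a higher hazard, lost and delayed events outweigh this and the error is inflated.

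**3. Size under the written rule.** The documents do not give the following, so they are assumptions: stop rates of 10% and 25%, stops spread evenly over months 0 to 6, hazard of men who stop relative to the others from 0.67 to 3, and a mean of 10 months from progression to death. The overall true median is held at 14 months, with 42 men and the test at 20 events. Simulated one-sided type I error against the nominal 10%, where repeat runs differ by up to about one percentage point:

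| Hazard ratio, men who stop vs others | 10% stop | 25% stop |
|---|---|---|
| 0.67 | about 6–7% | about 3% |
| 1 | about 9% | about 5–6% |
| 1.5 | about 11% | about 10% |
| 2 | about 12–13% | about 13–14% |
| 3 | about 13–14% | about 18–19% |

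With complete progression follow-up, the same set-up gives about 10–11%, and about 12% at 25% stops with a hazard ratio of 3. Part of the excess in that last setting therefore comes from mixing two hazards and not from the follow-up rule.

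**4. A second model.** This one uses 38 men, accrual over 21 months, a hazard that changes by a factor of 1 to 3 at the stop, median survival after progression of 9, 18.4 or 30 months, and 10% of PFS events being deaths. The written rule gives 8.3–12.8% at 10% stops and 6.9–18.6% at 25% stops. With complete progression follow-up, error is 8–10% in every setting. The two models agree on direction and size.

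**The case against.** Several points on the other side stand.

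- **The stop rate is borrowed.** The protocol gives none for this regimen. The 25% comes from its remark in Section 2.3 that "more than 25% of men discontinued due to toxicity" in the sunitinib trial, and the same section argues that tivozanib is better tolerated. At 10% stops the departure is a few percentage points on a phase 2 screen.
- **The direction is not known.** No section says that men who stop have a worse prognosis. With equal or better prognosis the written rule is conservative.
- **Some progression is caught.** The off-study visit includes history, examination, performance status, PSA and, where due, scans. Clinical progression counts as an event. Some men already progressing at the stop will therefore be recorded, which the simulations do not model.
- **Removal is not literal.** Section 5.5 keeps following these men for survival, and Section 9.1.4 does not forbid using a progression found off treatment. A reader might infer that later progression can never be recorded. The documents support only the narrower statement that nothing schedules or collects it.

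A reader might also infer an error rate as high as 36%. That figure arises only if deaths after the stop are left out of PFS. The opening of Section 9 could suggest this by naming only disease-related deaths, but Sections 9.1.4 and 14.1 count any death without documented progression. The wording needs reconciling, but it does not establish that rule.

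Finally, routine-care progression dates have ascertainment problems of their own, and no calculation shows that they restore exactly 10%.

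**Conclusion.** The point holds in limited form. As written, the plan leaves progression unscheduled after a stop for toxicity or intercurrent illness. It then treats living and deceased men differently in a test that depends on exposure per event. The error departs from the nominal 10%: about 5% (same hazard as the others) to 19% (three times the hazard) if 25% stop, and about 9% to 14% if 10% stop. It is below 5% at 25% stops if men who stop have a better prognosis.

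These sizes rest on the assumed stop rates, timing, hazards and time from progression to death. A reader might conclude that the error is always inflated or without bound. The documents do not support that: the direction depends on prognosis, and under the written rule the departure at 10% stops is modest. What the trial lacks is the information to tell which case applies.

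**What to change.** - In Sections 5.5 and 5.6, separate leaving treatment from leaving the study for data collection. No treatment or stopping rule needs to change for this.
- At the existing 3-monthly contacts, record the date and type of any progression found in routine care and the start of any new anticancer therapy. Continue until progression, death, withdrawal of consent or end of follow-up, and use these progression dates in PFS.
- Pre-specify one sensitivity analysis that counts discontinuation for toxicity, or start of new therapy, as a PFS event. Section 5.6 already requires the reason for removal.
- Reconcile the disease-death wording at the opening of Section 9 with the any-death wording of Sections 9.1.4 and 14.1.
- Reconcile Sections 5.1.2 and 6.2 on whether a long hold ends study treatment or study participation.

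The cost is protocol wording and a few fields on the follow-up and survival form already listed in Section 12.1, with no study-mandated scans. Routine-care assessments are less standardised than study scans, so the bias is reduced and not removed.

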6. EXPECTED TOXICITIES AND DOSING DELAYS/DOSE MODIFICATIONS

All men will be initially treated at starting doses of 1.5 mg/day of tivozanib and 160 mg/day of enzalutamide.

6.1 Anticipated Toxicities of Tivozanib

In the phase 3 trial of tivozanib in renal cell carcinoma, 66.9% of the 272 subjects treated with tivozanib experienced at least one treatment-related adverse event. The most common adverse events were: hypertension (44.9%), dysphonia (21.7%), asthenia/fatigue (18.4%), diarrhea (12.1%), dyspnea (5.9%), anorexia (4.8%), cough (4.8%), stomatitis (4.4%) and hand-foot syndrome (4.0%)³.

In this trial, 16 subjects experienced adverse events leading to death, and one of these AEs leading to death (hypertension) was considered probably related to study treatment. Three of the AEs were considered possibly related to study treatment (cerebrovascular, pulmonary embolism, post-procedural hemorrhage) and the remaining were unlikely related or unrelated to tivo.

6.2 Tivozanib Dose Modification

Clinical judgment will be used to determine appropriate management of the subject experiencing any adverse event (AE). The suggested criteria for dose modification for tivozanib hydrochloride drug-related AEs (excluding hypertension) are summarized in the table below.

Tivozanib Hydrochloride Dose Modification Guidelines for Drug-Related Adverse Events

| Drug-Related Adverse | Action Taken | Subsequent Dosing Modification |
|-----------------------------|--|---|
| Events (excluding | | |
| Hypertension ^a) | | |
| Grade 1 | No dose interruption, or reduction required; adverse event management is at the discretion of the Investigator | None required; Dosing may continue at the same dose |
| Grade 2 | No dose interruption, or reduction required; adverse event management is at the discretion of the Investigator | None required; Dosing may continue at the same dose |
| Grade 3 | Interrupt dosing until toxicity resolves to baseline. | Dosing may resume at same dose or reduced dose at the discretion of the Investigator (see below for dose reduction guidelines). |
| Grade 4 | Interrupt dosing until toxicity resolves to baseline. | Dosing may resume at same dose or reduced dose at the discretion of the investigator (see below for dose reduction guidelines). |

^a Hypertension must be treated as described in Section 6.2.1 prior to any dose modification

If a patient experiences unacceptable toxicity related to tivozanib at 1 mg/day, he should be removed from study. Once the dose of tivozanib is reduced, it should not be re-escalated throughout the study.

Subjects with clinically significant Grade 3/4 AEs that are assessed as possibly, probably or definitely study drug-related by the Investigator should have their dose interrupted to allow for resolution of toxicities to baseline. The exception is HTN, which must first be treated as described in Section 6.2.1 prior to any dose modification. Tivozanib may be held for up to 4 weeks. If any drug-related toxicity results in interruption of > 4 weeks, the subject should be discontinued from the study.

Dose escalation of tivozanib above 1.5 mg/day will not be allowed.

Dose delays and modifications will be made using the following recommendations. Toxicity assessments will be done using the CTEP Active Version of the NCI Common Terminology Criteria for Adverse Events (CTCAE) which is identified and located on the CTEP website at: http://ctep.cancer.gov/protocolDevelopment/electronic applications/ctc.htm.

If possible, symptoms should be managed symptomatically. In the case of toxicity, appropriate medical treatment should be used (including anti-emetics, anti-diarrheals, etc.).

All adverse events experienced by participants will be collected from the time of the first dose of study treatment, through the study and until the final study visit. Participants continuing to

experience toxicity at the off study visit may be contacted for additional assessments until the toxicity has resolved or is deemed irreversible.

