5.1.2 Day 1 of Every 3rd Cycle

The following data should be collected on Day 1 (+/- 3 days) of every 3rd cycle (see Schedule of Events):

- History and physical examination
- ECOG performance status
- Vital signs (including blood pressure, body temperature, heart rate and respiratory rate)
- Complete blood count
- Serum chemistries
- Thyroid function test (TSH only; every odd number Cycle beyond Cycle 1 up to Cycle 46 and then every 3rd Cycle)
- Urinalysis (urine protein only)
- Serum PSA
- Concomitant medications
- Adverse event assessments
- Study drug diary

[Note: If ECOG performance status, physical examination, hematology, serum chemistry, coagulation studies, and urinalysis were measured/performed within 7 days prior to Cycle 1, Day 1, they need not be repeated at that visit.]

If any treatment-related grade ≥ 3 non-hematologic or grade ≥ 4 hematologic adverse events are observed, then treatment should be held until resolution of the event(s) to \leq grade 2. The attribution of the events to either or both of the study drugs will be at the discretion of the treating physician, and only the responsible drug should be held. Doses that are held will not be

made up, and the cycle number and cycle day will continue chronologically regardless of whether treatment is held.

If either study drug is held for \geq 4 weeks, regardless of cause, then the patient should be removed from study treatment.

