8. STUDY CALENDAR

Baseline evaluations are to be conducted within 3 weeks prior to start of protocol therapy. Subsequent evaluations should be carried out on Day 1 of subsequent cycles (+/- 3 days) every 12 weeks from Cycle 46 on. Radiographic evaluations including bone and abdominal/pelvic CT scans should be conducted at baseline and every 24 weeks from Cycle 46 on.

| | Pre- Study | Cycle 1 Day 1 ^x | Cycle 2 to Cycle 45, Day 1 ^x | Day 1 Cycles ≥ 46, Every 12 Weeks ^x | Off Study ^b |
|---|---------------|-------------------------------|---|--|------------------------|
| Treatment Schedule: | | | | | |
| Tivozanib | | X (days 1-21) | X (days 1-21) | X (days 1-21) | |
| Enzalutamide | | X (Days 1-28) | X (days 1-28) | X (days 1-28) | |
| Informed consent | X | | | | |
| Demographics | X | | | | |
| Medical/Interval history | X | X | X | X | X |
| Concurrent meds | X | X | X | X | X |
| Physical exam | X | X | X | X | X |
| Vital signs/ BP | X | X | X | X | X |
| Performance status | X | X | X | X | X |
| Serum PSA | X | | X | X | X |
| PT, PT/INR, and PTT | X | | | | |
| CBC w/diff, plts | X | X | X | X | X |
| Serum chemistry ^a | X | X | X | X | X |
| Serum testosterone | X | | | | |
| Thyroid Function (TSH only) | X | | X (odd cycles) | X | |
| Urinalysis (urine protein only) | X | X | X | X | X |
| Chest xray | X | | as clinicall | y indicated | |
| Bone scan and abdominal/pelvis CT scans | X | Rep | Repeat scans every 24 weeks | | X ^c |
| EKG | X | | | | |
| Adverse Event Evaluation | X | Х | | | -X |
| Survival follow-up | | | | | X ^d |

x: ± 3 days for treatment or assessment requirement

MEASUREMENT OF EFFECT

a: Sodium, potassium, chloride, BUN, creatinine, glucose, albumin, total protein, total bilirubin, alkaline phosphatase, SGOT [AST], SGPT [ALT]

b: Off-study evaluation should occur within 30 days after the last dose of study treatment c: Post-treatment scans will be performed if an assessment has not been performed within the prior 6 weeks

d: Follow for survival information every 3 months until death, up to 2 years after discontinuing therapy, or patient lost to follow-up

The primary endpoint of the study is progression free survival (PFS). Secondary clinical endpoints will include safety, overall survival, time to PSA progression, PSA response rate and objective response rate.

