11.2 Adverse Event Characteristics

CTCAE term (AE description) and grade: The descriptions and grading scales found in the revised NCI Common Terminology Criteria for Adverse Events (CTCAE) version 4.0 (Appendix D) will be utilized for AE reporting. If specific grading is not available in the CTCAE for a particular AE's severity/intensity, the Investigator is to revert to the general definitions of Grade 1 through 5 and use his/her best medical judgment. The 5 general grades are: Grade 1 = mild, Grade 2 = moderate, Grade 3 = severe, Grade 4 = life-threatening or disabling, Grade 5 = death related to AE.

Attribution of the AE:

Investigators are required to assess whether there is a reasonable possibility that tivozanib hydrochloride caused or contributed to the adverse event. The following general guidance may be used.

- Definite The AE *is clearly related* to the study treatment.
- Probable The AE *is likely related* to the study treatment.
- Possible The AE *may be related* to the study treatment.
- Unlikely The AE *is doubtfully related* to the study treatment.
- Unrelated The AE is clearly NOT related to the study treatment.

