11.3 Procedures for Reporting AEs and SAEs

Adverse events, both serious and non-serious, and deaths that occur during the patient's study participation (from time of written informed consent through 30 days after receiving the last dose of tivozanib hydrochloride) will be documented. All subjects receiving at least 1 dose of tivozanib hydrochloride, whether completing the treatment period or not, should be followed for

30 days after the last dose of tivozanib hydrochloride. New AEs and changes in ongoing AEs or those with an unknown outcome must be followed for 30 days after the last dose of tivozanib hydrochloride. All SAEs should be monitored until they are resolved or are clearly determined to be due to a patient's stable or chronic condition or intercurrent illness(es). The Investigator will determine the seriousness, intensity, and causality of an adverse event associated with the use of the study drug (ie, events where there is a reasonable possibility that the event may have been caused by the study drug).

All SAEs should be recorded on a Medwatch Form 3500A and sent to the FDA, to AVEO Pharmacovigilance/Drug Safety, National Comprehensive Cancer Network (NCCN), and to the Principal Investigator/Study Coordination Center (if applicable).

SAE Reporting Contact Information

Food and Drug Administration Center for Drug Evaluation and Research Division of Oncology Products [name]

SAE Reporting Contact Information

Please submit SAE Reports to Parexel GPPG via email ([contact]). If submission via email is not possible or delayed then submission via fax (NA [contact]) is acceptable.

Pharmacovigilance/Drug Safety AVEO Pharmaceuticals, Inc [name] [contact]

E-mail: [contact]

SAE Reporting Contact Information

National Comprehensive Cancer Network (NCCN) [contact] Email: [contact]

SAE Reporting Contact Information

[name]/Massachusetts General Hospital Cancer Center [contact] [contact] Email: [contact]

Medwatch 3500A Reporting Guidelines:

In addition to completing appropriate demographic and suspect medication information, the report should include the following information within the Event Description (Section 5) of the Medwatch Form 3500A (Appendix E):

- Treatment regimen (dosing, frequency, combination therapy)
- Protocol description (include number if assigned)
- Description of event, severity, treatment, and outcome, if known

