- Supportive diagnostic and laboratory results
- Investigator's assessment of the relationship of the SAE to each investigational product and suspect medication

Follow-up information

Additional information may be added to a previously submitted report by any of the following methods:

- Adding to the original Medwatch Form 3500A and submitting it as follow-up
- Adding supplementary summary information and submitting it as follow-up with the original Medwatch Form 3500A
- Summarizing new information and faxing it with a cover letter including subject identifiers (ie, DOB, initials, subject number), protocol description and number, suspect drug, brief adverse event description, and notation that additional or follow-up information is being submitted

Occasionally, AVEO Pharmacovigilance/Drug Safety may contact the reporter for additional information, clarification, or current status of the subject for whom the adverse event was reported.

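### Sections 6.2 and 11.3 set different adverse-event windows, and the only fixed 30-day tail runs from the last tivozanib dose, so some late events after enzalutamide may be missed

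*Combined protocol and SAP*

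**What the plan says.** Two sections define when adverse events are collected.

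- Section 6.2: all adverse events are "collected from the time of the first dose of study treatment, through the study and until the final study visit".
- Section 11.3: serious and non-serious events and deaths are documented "from time of written informed consent through 30 days after receiving the last dose of tivozanib hydrochloride".

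The study calendar (section 8) fixes the last visit only loosely: "Off-study evaluation should occur within 30 days after the last dose of study treatment". Section 11.5, on deaths reported regardless of cause, also uses 30 days from the last tivozanib dose, and adds later deaths thought to be drug-related.

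The two drugs do not stop together. The calendar gives tivozanib on days 1–21 and enzalutamide on days 1–28 of each cycle. When toxicity requires a hold, section 5.1.2 says "only the responsible drug should be held". It removes a man from study treatment once either drug has been held for 4 weeks or more.

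On causality, section 11.2 opens with "Investigators are required to assess whether there is a reasonable possibility that tivozanib hydrochloride caused or contributed to the adverse event". The five categories below that sentence grade the relation "to the study treatment". For reports of serious events, section 11.3 asks for the "Investigator's assessment of the relationship of the SAE to each investigational product and suspect medication". Section 5.1.2 says "The attribution of the events to either or both of the study drugs will be at the discretion of the treating physician".

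**The concern.** Tolerability of the combination is part of the study objective (section 1) and a secondary objective (1.3), and the plan says that the combination has not been tested before. The toxicity analysis in section 14.3 covers all treated patients but gives no collection window, so any conflict between 6.2 and 11.3 passes into the toxicity tables. Two sites could follow the protocol and collect over different periods.

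The anchor matters separately from the conflict. Enzalutamide has risks of its own; section 6.3 records five seizures with it and none with placebo. A tail counted from the last tivozanib dose gives less than 30 days after enzalutamide whenever enzalutamide stops later, which is the normal order within a cycle.

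The causality sentence raises a related question. The run-in rule turns on treatment-related events of grade 3 or higher but does not define that term. An investigator who follows the lead sentence of 11.2 literally would record no judgement about enzalutamide for a non-serious event.

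**Working it through.** **1. The plan's own toxicity figures.** Section 14.3 gives 88% for seeing at least one event at a true rate of 5% in 42 patients. 1 − 0.95^42 = 0.884, which agrees. It gives 27% as the greatest width of a 90% interval. The largest exact (Clopper–Pearson) width over 0 to 42 events is 0.271, which agrees. The 88% takes it that every event is captured.

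**2. The windows side by side.**

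| | Start | End |
|---|---|---|
| 6.2 | first dose | final study visit |
| 11.3 | consent | last tivozanib dose + 30 days |
| 11.5 (deaths from any cause) | enrollment | last tivozanib dose + 30 days |

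The start points differ, but no on-treatment event is lost by that. Sections 5.1 and 8 already call for an adverse event assessment before treatment, which fits a start at consent. The end points are where events can be lost.

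**3. The gap between the drugs.** Let G be the days from the last tivozanib dose to the last enzalutamide dose.

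- Ordinary cycle: G = 28 − 21 = 7, and the tail leaves 30 − 7 = 23 days after enzalutamide.
- Week off followed by a tivozanib hold of just under 4 weeks (27 days) with enzalutamide continued: G = 7 + 27 = 34. The tail ends 34 − 30 = 4 days before enzalutamide stops.

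The second case counts the hold in calendar days from the first omitted scheduled dose. If the week off counted as part of the hold, G would be at most 27 and 30 − 27 = 3 days would remain.

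**4. What is uncovered when both windows are applied together.** Take the final visit in 6.2 to be the off-study visit, V days after the last dose of either drug (V from 0 to 30). Coverage after the last enzalutamide dose is the larger of V and 30 − G. Of the 30 days after that dose, the uncovered part is the smaller of 30 − V and G.

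| Case | V = 0 | V = 15 | V = 30 |
|---|---|---|---|
| G = 7 | 7 days | 7 days | 0 |
| G = 34 | 30 days | 15 days | 0 |

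The values of V are illustrative; the documents set only the range. If a site used 6.2 alone, 30 − V days would be uncovered whatever G is.

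**5. The run-in.** The rule uses the first month of treatment (sections 1.1, 5 and 14.1). For men on treatment that month lies inside both windows, so their conflict cannot change the run-in stopping probabilities. Only attribution could.

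**6. What incomplete capture would do.** The documents give no capture rate. As an assumption, with 95%, 90%, 80% or 70% of events captured, the 0.884 in step 1 becomes 0.870, 0.855, 0.820 or 0.776 (for 90%: 1 − (1 − 0.045)^42 = 0.855). This is a range of what-ifs, not an estimate.

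**The case against.** The strongest reply is that the windows are cumulative. Nothing in 6.2 lets a site stop before the end set in 11.3, and nothing in 11.3 cancels the off-study visit, which includes an adverse event assessment (5.1.3). Section 6.2 therefore covers all time on enzalutamide, including the case in which the tivozanib tail has expired. Other provisions narrow the gap further: ongoing toxicity may be followed to resolution (6.2), serious events are monitored until resolved or explained (11.3), the manufacturer must be told of all serious events (11.4), and later drug-related deaths are reportable (11.5). All of this stands, and it is why the exposure is mainly to new non-serious events. It does not close the gap, because step 4 already applies both windows.

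On causality, the reply is also largely right. The scale in 11.2, the serious-event reports and section 5.1.2 all reach beyond tivozanib. The fault is inconsistent wording, felt mainly for non-serious events. The toxicity endpoint (9.1.1, 14.3) has no attribution filter, so an event blamed on enzalutamide alone is still counted there.

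A reader might go further and infer that toxicity will be under-counted. The documents support only that it may be. Three figures might also tempt:

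- **30 days lost per man.** This is a bound. As a general loss it would require 11.3 to be ignored.
- **Only 2 days of follow-up after enzalutamide (30 − 28).** A 28-day hold already triggers removal under 5.1.2, and the figure leaves out the off-study visit.
- **26–35% of observation time**, from 30/(84 + 30) and 30/(56 + 30). This supposes only two or three cycles of treatment. If treatment lasted about as long as the plan's median PFS of 14 to 22.4 months (426 to 682 days at 30.44 days a month), the share would be 30/456 = 6.6% to 30/712 = 4.2%. A share of time is in any case not a share of events.

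**Conclusion.** The concern holds in a limited form. Sections 6.2 and 11.3 conflict, and the only fixed tail in 11.3, repeated in 11.5, is tied to one drug of a two-drug regimen. With both windows applied, new events after the off-study visit and within 30 days of the last enzalutamide dose may go uncollected. That is up to 7 days per man in an ordinary cycle, and up to the full 30 in the extreme case of a long tivozanib hold with a visit on the last dosing day. These are bounds that rest on how a hold is counted and on the final visit being the off-study visit. The number of events missed cannot be derived from the documents.

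The windows do not affect the run-in, and the conclusion does not touch the PFS analysis. The wording of 11.2 should be brought into line with the rest of the protocol. This is a stated rule that should be corrected, at low cost, in a combination whose safety is being described for the first time.

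**What to change.** - In 6.2, 11.3 and 11.5, state one window: from consent to 30 days after the last dose of either study drug, whichever is later.
- In 11.2, name both drugs in the lead sentence and record relatedness separately for tivozanib and for enzalutamide for every adverse event.
- Wherever the run-in rule appears (1.1, 5 and 14.1), state that a treatment-related event is one related to either drug.
- In 14.3, cite the same window for the toxicity tables.

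The cost is wording and one extra causality field. Against 11.3 as it stands, the end of follow-up moves later by the gap between the drugs: 7 days in an ordinary cycle and up to about 34 after a long hold. For some men that means a follow-up contact after the off-study visit. No dose or treatment rule changes.
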